8.3 ADVERSE EVENTS AND SERIOUS ADVERSE EVENTS

8.3.1 DEFINITION OF ADVERSE EVENTS (AE)

"Adverse event" means any untoward medical occurrence associated with the use of an intervention in humans, whether or not considered intervention-related (21 CFR 312.32 (a)).

8.3.2 DEFINITION OF SERIOUS ADVERSE EVENTS (SAE)

An adverse event (AE) or suspected adverse reaction is considered "serious" if, in the view of either the investigator or sponsor, it results in any of the following outcomes: death, a life-threatening adverse event, inpatient hospitalization or prolongation of existing hospitalization, a persistent or significant incapacity or substantial disruption of the ability to conduct normal life functions, or a congenital anomaly/birth defect. Important medical events that may not result in death, be life-threatening, or require hospitalization may be considered serious when, based upon appropriate medical judgment, they may jeopardize the participant and may require medical or surgical intervention to prevent one of the outcomes listed in this definition. Examples of such medical events include allergic bronchospasm requiring intensive treatment in an emergency room or at home, blood dyscrasias or convulsions that do not result in inpatient hospitalization, or the development of drug dependency or drug abuse. Examples relevant to this trial include adverse effects of GI endoscopy and its associated sedation that result in hospitalization, or gastrointestinal hemorrhage or vascular events in subjects receiving indomethacin.

8.3.3 CLASSIFICATION OF AN ADVERSE EVENT

8.3.3.1 SEVERITY OF EVENT

For adverse events (AEs) the following guidelines will be used to describe severity.

- **Mild** – Events require minimal or no treatment and do not interfere with the participant’s daily activities.
- **Moderate** – Events result in a low level of inconvenience or concern with the therapeutic measures. Moderate events may cause some interference with functioning.
- **Severe** – Events interrupt a participant’s usual daily activity and may require systemic drug therapy or other treatment. Severe events are usually potentially life-threatening or incapacitating. Of note, the term “severe” does not necessarily equate to “serious”.

8.3.3.2 RELATIONSHIP TO STUDY INTERVENTION

All adverse events (AEs) must have their relationship to study intervention assessed by the clinician who examines and evaluates the participant based on temporal relationship and his/her clinical judgment. The degree of certainty about causality will be graded using the categories below. In a clinical trial, the study product must always be suspect.

- **Definitely Related** – There is clear evidence to suggest a causal relationship, and other possible contributing factors can be ruled out. The clinical event, including an abnormal laboratory test result, occurs in a plausible time relationship to study intervention administration and cannot be explained by concurrent disease or other drugs or chemicals. The response to withdrawal of the study intervention (dechallenge) should be clinically plausible. The event must be pharmacologically or phenomenologically definitive, with use of a satisfactory rechallenge procedure if necessary.
- **Probably Related** – There is evidence to suggest a causal relationship, and the influence of other factors is unlikely. The clinical event, including an abnormal laboratory test result, occurs within a reasonable time after administration of the study intervention, is unlikely to be attributed to concurrent disease or other drugs or chemicals, and follows a clinically reasonable response on withdrawal (dechallenge). Rechallenge information is not required to fulfill this definition.
- **Potentially Related** – There is some evidence to suggest a causal relationship (e.g., the event occurred within a reasonable time after administration of the trial medication). However, other factors may have contributed to the event (e.g., the participant’s clinical condition, other concomitant events). Although an AE may rate only as “possibly related” soon after discovery, it can be flagged as requiring more information and later be upgraded to “probably related” or “definitely related”, as appropriate.
- **Unlikely to be related** – A clinical event, including an abnormal laboratory test result, whose temporal relationship to study intervention administration makes a causal relationship improbable (e.g., the event did not occur within a reasonable time after administration of the study intervention) and in which other drugs or chemicals or underlying disease provides plausible explanations (e.g., the participant’s clinical condition, other concomitant treatments).
- **Not Related** – The AE is completely independent of study intervention administration, and/or evidence exists that the event is definitely related to another etiology. There must be an alternative, definitive etiology documented by the clinician.

8.3.3.3 EXPECTEDNESS

Drs. [name] and [name], the study co-PIs, will be responsible for determining whether an adverse event (AE) is expected or unexpected. An AE will be considered unexpected if the nature, severity, or frequency of the event is not consistent with the risk information previously described for the study intervention.

Expected adverse events include (but are not limited to) allergic reactions to study medication, adverse effects of indomethacin such as upset stomach, vomiting, heartburn, diarrhea, constipation, bloating, flatulence, rash, itching, tinnitus, lightheadedness. Serious adverse events may include gastrointestinal ulceration, bleeding, perforation or obstruction as well as renal insufficiency or known complications of GI endoscopy. However the protocol has been designed to minimize the risk of these SAEs by excluding persons with risk factors for endoscopic adverse events, NSAID-induced gastrointestinal ulceration or renal insufficiency.

8.3.4 TIME PERIOD AND FREQUENCY FOR EVENT ASSESSMENT AND FOLLOW-UP

The occurrence of an adverse event (AE) or serious adverse event (SAE) may come to the attention of study personnel during study visits or weekly scheduled telephone interviews of a study participant, by communication to study staff initiated by the study participant, or when a participant presents for medical care.

All AEs including local and systemic reactions not meeting the criteria for SAEs will be captured on the appropriate case report form (CRF). Information to be collected includes event description, time of onset, clinician's assessment of severity, relationship to study product (assessed only by those with the training and authority to make a diagnosis), and time of resolution/stabilization of the event. All AEs occurring while on study must be documented appropriately regardless of relationship. All AEs will be followed to adequate resolution.

Any medical condition that is present at the time that the participant is screened will be considered as baseline and not reported as an AE. However, if the study participant's condition deteriorates at any time during the study, it will be recorded as an AE.

Changes in the severity of an AE will be documented to allow an assessment of the duration of the event at each level of severity to be performed. AEs characterized as intermittent require documentation of onset and duration of each episode.

The study coordinators will record all reportable events with start dates occurring any time after informed consent is obtained until 7 (for non-serious AEs) or 30 days (for SAEs) after the last day of study participation. At each study visit, the investigator will inquire about the occurrence of AE/SAEs since the last visit. Events will be followed for outcome information until resolution or stabilization.

8.3.5 ADVERSE EVENT REPORTING

AEs will be reported to the study PIs within 24 hours, and summarized in quarterly reports to the study DSMB as well as annual reports to the IRB, FDA and NIH. Furthermore, AEs will be reported to additional regulatory agencies (such as the FDA) if and as required.

8.3.6 SERIOUS ADVERSE EVENT REPORTING

According to 21 CFR 312.64(b), “An investigator must immediately report to the sponsor any serious adverse event, whether or not considered drug related, including those listed in the protocol or investigator brochure and must include an assessment of whether there is a reasonable possibility that the drug caused the event. Study endpoints that are serious adverse events (e.g., all-cause mortality) must be reported in accordance with the protocol unless there is evidence suggesting a causal relationship between the drug and the event (e.g., death from anaphylaxis). In that case, the investigator must immediately report the event to the sponsor...”

According to 21 CFR 312.32(c)(1), “the sponsor must notify FDA and all participating investigators...in an IND safety report of potential serious risks, from clinical trials or any other source, as soon as possible, but in no case later than 15 calendar days after the sponsor determines that the information qualifies for reporting... In each IND safety report, the sponsor must identify all IND safety reports previously submitted to FDA concerning a similar suspected adverse reaction, and must analyze the significance of the suspected adverse reaction in light of previous, similar reports or any other relevant information. The sponsor must report any suspected adverse reaction that is both serious and unexpected. The sponsor must report an adverse event as a suspected adverse reaction only if there is evidence to suggest a causal relationship between the drug and the adverse event, such as:

- (A) A single occurrence of an event that is uncommon and known to be strongly associated with drug exposure (e.g., angioedema, hepatic injury, Stevens-Johnson Syndrome);*
- (B) One or more occurrences of an event that is not commonly associated with drug exposure, but is otherwise uncommon in the population exposed to the drug (e.g., tendon rupture);*
- (C) An aggregate analysis of specific events observed in a clinical trial (such as known consequences of the underlying disease or condition under investigation or other events that commonly occur in the study population independent of drug therapy) that indicates those events occur more frequently in the drug treatment group than in a concurrent or historical control group.”*

Furthermore, according to 21 CFR 312.32(c)(2), “the sponsor must also notify FDA of any unexpected fatal or life-threatening suspected adverse reaction as soon as possible but in no case later than 7 calendar days after the sponsor's initial receipt of the information.”

The study clinicians will immediately report to the DSMB any serious adverse event, whether or not considered study intervention related, including those listed in the protocol or ICF, and must include an assessment of whether there is a reasonable possibility that the study intervention caused the event. Study endpoints that are serious adverse events (e.g., all-cause mortality) must be reported in accordance with the protocol unless there is evidence suggesting a causal relationship between the study intervention and the event (e.g., death from anaphylaxis). In that case, the investigator must immediately report the event to the sponsor.

All serious adverse events (SAEs) will be followed until satisfactory resolution or until the site investigator deems the event to be chronic or the participant is stable. Other supporting documentation of the event may be requested by the DSMB, IRB, FDA, or NIH and should be provided as soon as possible.

The study PI is responsible for notifying the Food and Drug Administration (FDA) of any unexpected fatal or life-threatening suspected adverse reaction as soon as possible, but in no case later than 7 calendar

days after the sponsor's initial receipt of the information. In addition, the sponsor must notify FDA and all participating investigators in an Investigational New Drug (IND) safety report of potential serious risks, from clinical trials or any other source, as soon as possible, but in no case later than 15 calendar days after the PI determines that the information qualifies for reporting.

SAEs will be summarized in quarterly reports to the DSMB and in annual reports to the IRB, NIH and FDA.

8.3.7 REPORTING EVENTS TO PARTICIPANTS

A de-identified summary of AEs and SAEs will be included in published results of this trial, and this information will be made available to study subjects.

8.3.8 EVENTS OF SPECIAL INTEREST

Not applicable.

8.3.9 REPORTING OF PREGNANCY

If a study participant reports that they are pregnant they will be advised to immediately discontinue study drug use. Study endoscopic procedures will not be performed on pregnant participants. Pregnant participants will be withdrawn from the study.

8.4 UNANTICIPATED PROBLEMS

8.4.1 DEFINITION OF UNANTICIPATED PROBLEMS (UP)

The Office for Human Research Protections (OHRP) considers unanticipated problems involving risks to participants or others to include, in general, any incident, experience, or outcome that meets all of the following criteria:

- Unexpected in terms of nature, severity, or frequency given (a) the research procedures that are described in the protocol-related documents, such as the Institutional Review Board (IRB)-approved research protocol and informed consent document; and (b) the characteristics of the participant population being studied;
- Related or possibly related to participation in the research ("possibly related" means there is a reasonable possibility that the incident, experience, or outcome may have been caused by the procedures involved in the research); and
- Suggests that the research places participants or others at a greater risk of harm (including physical, psychological, economic, or social harm) than was previously known or recognized.

An incident, experience, or outcome that meets the definition of an UP may warrant consideration of changes to the protocol or consent in order to protect the safety, welfare, or rights of participants or

others. Other UPs may warrant corrective actions at a specific study site. Examples of corrective actions or changes that might need to be considered in response to an UP include:

- Modification of inclusion or exclusion criteria to mitigate the newly identified risks
- Implementation of additional safety monitoring procedures
- Suspension of enrollment of new participants or halting of study procedures for enrolled participants
- Modification of informed consent documents to include a description of newly recognized risks
- Provision of additional information about newly recognized risks to previously enrolled participants.

8.4.2 UNANTICIPATED PROBLEM REPORTING

The investigator will report unanticipated problems (UPs) to the reviewing Institutional Review Board (IRB) and to the DSMB. The UP report will include the following information:

- Protocol identifying information: protocol title and number, PI's name, and the IRB project number;
- A detailed description of the event, incident, experience, or outcome;
- An explanation of the basis for determining that the event, incident, experience, or outcome represents an UP;
- A description of any changes to the protocol or ICF, or other corrective actions that have been taken or are proposed in response to the UP.

To satisfy the requirement for prompt reporting, UPs will be reported using the following timeline:

- UPs that are serious adverse events (SAEs) will be reported to the DSMB immediately, and to the IRB within 7 days of the investigator becoming aware of the event.
- Any other UP will be reported to the DSMB within 30 days of the investigator becoming aware of the problem, and summarized in quarterly reports to DSMB and annual reports to the IRB, FDA and NIH.
- All UPs should be reported to appropriate institutional officials (as required by an institution's written reporting procedures), the supporting agency head (or designee), and the Office for Human Research Protections (OHRP) within 3 months of the IRB's receipt of the report of the problem from the investigator.

8.4.3 REPORTING UNANTICIPATED PROBLEMS TO PARTICIPANTS

UPs that are SAEs may require revision of the study informed consent form (ICF). In that case, study participants who are active participants (taking study drug or scheduled for study endoscopy) will be informed of the revisions to the ICF and re-consented.

9 STATISTICAL CONSIDERATIONS

9.1 STATISTICAL HYPOTHESES

Primary Endpoint:

- Decrease in mean pancreatic juice PGE₂ concentration after indomethacin treatment, to no more than 66% of baseline, and statistically significant in comparison to placebo.

Secondary Efficacy Endpoints:

- Changes in salivary and blood PGE₂ concentrations after study drug administration will have statistically significant correlation with changes in PJ PGE₂ concentrations and blood IN levels.
- Salivary and blood PGE₂ concentrations will have statistically significant correlation with PJ PGE₂ concentrations.
- Improvement in pain and quality of life of study participants will have statistically significant correlation with post-treatment changes in PJ PGE₂ concentrations.
- Exploratory analysis of molecular analytes (cytokine and microbiome) in blood and saliva will be done to measure effect of IN administration.

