2 INTRODUCTION

2.1 STUDY RATIONALE

Chronic pancreatitis (CP) is a chronic fibro-inflammatory disease. There is no medical therapy that modifies the disease course of CP. Our **long-term goal is to identify effective disease-modifying therapeutic strategies for CP**. Chronic inhibition of pancreatic prostaglandin E₂ (PGE₂) production is one such promising strategy. Indomethacin (IN) is an inhibitor of COX-2 and suppresses systemic PGE₂ production, but the pharmacology of IN in human pancreas is unknown. This study will determine whether a standard clinical oral dose of IN, administered for 4 weeks, decreases PGE₂ concentrations in pancreatic juice, setting the stage for a subsequent large-scale clinical trial of IN in CP.

PGE₂ is produced at sites of inflammation by the cyclooxygenase-2 enzyme (COX-2), which is overexpressed in the pancreas of humans with CP. PGE₂ is a potent mediator of pancreatic chronic inflammation and stellate cell activity. Pancreas juice (PJ) PGE₂ concentrations are elevated in patients with CP and suspected early or “minimal change” CP (MCCP) compared to normal volunteers. PJ can be collected during GI endoscopy and subsequently assayed for PGE2, providing a minimally invasive method of assessing pancreatic COX-2 activity. Rectally administered IN prevents acute post-ERCP pancreatitis, although the mechanism by which it prevents human acute pancreatitis is uninvestigated.

Chronic inhibition of pancreatic COX-2 is a promising therapeutic strategy for CP, but there are no data regarding the drug, dose, and route of administration required for steady-state inhibition of human pancreatic COX-2 activity.

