with PJ PGE₂ levels; if correlation is high it may be possible to use these non-invasive biospecimens as surrogates for pancreatic juice in future studies.

Preliminary Data: We measured pancreas juice (PJ) PGE₂ levels in patients with CP (n=10), minimal change CP (MCCP) (n=25), and normal volunteers (n=10).¹⁷ There were statistically significant elevations of PJ PGE₂ in both MCCP and CP compared to normal volunteers (**Figure 2**). PJ PGE₂ (at a cutoff of 300 pg/ml) had a diagnostic accuracy of 92% for MCCP, compared to 62% for PJ bicarbonate concentration (at a cutoff of 80 mEq/L). These findings suggest that PJ PGE₂ levels may serve as a biomarker for pancreatic inflammation.

Rationale for study drug dosage:

There is no published data on the effect of IN on human pancreatic COX-2 activity. Usual clinical doses of oral indomethacin are 25-50 mg BID to TID. This study's dose of oral IN was chosen based on standard clinical dosing, published literature showing that similar blood levels are achieved with oral vs rectal administration, and the fact that steady-state administration of IN 50 mg BID orally should result in higher blood and tissue drug levels than 100 mg administered rectally once. Common side effects of IN such as dyspepsia are often dose related. Five doses of drug are required to achieve pharmacological steady state.

NIH-sponsored CPDPC Consortium: This protocol leverages resources of the NIH-funded, U01 Chronic Pancreatitis, Diabetes, and Pancreatic Cancer (CPDPC) Consortium. An overriding objective of CPDPC is “to encourage translational research focusing upon elucidating the pathogenesis that will provide a basis for understanding the natural history and developing means of diagnosis, treatment and clinical management of chronic pancreatitis”. Mayo Clinic Rochester ([name] – PI) and Ohio State University ([name] – co-PI) are members of the CPDPC, which funds principal investigator and study staff time at these institutions, providing a unique collaborative infrastructure for the proposed trial.

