9.3 POPULATIONS FOR ANALYSES

Given the small sample size of this pilot study, the entire study population completing the study protocol will be utilized for most analyses. Per-Protocol analysis will be used primarily (e.g., participants who took at least 80% of study intervention for 80% of the days within the treatment period).

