9.4.2 ANALYSIS OF THE PRIMARY EFFICACY ENDPOINT(S)

For the Primary Endpoint/Specific Aim 1, the primary analysis will be a linear random intercept model that incorporates PJ PGE₂ data from both baseline and day 28 from all randomized patients. Transformation will be used as appropriate to reduce the skewness of data and satisfy modeling assumption. The model includes randomized groups, time, and their interactions as fixed effect covariates, from which the mean change in PJ PGE₂ will be estimated for each randomized group. Effects of additional covariates, such as sex and sites, will be explored. The intra-subject correlation will be estimated from the variances of the random intercepts and residuals. Other outcome variables, such as other biomarkers and questionnaire data, can be analyzed in a similar way. The estimates about the variability of data and intrasubject correlations will be useful for designing a subsequent larger study.

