9.4.3 ANALYSIS OF THE SECONDARY ENDPOINT(S)

For Secondary Endpoints/Specific Aim 2, we will use multivariate analysis of variance model (MANOVA) with repeated measures. The multivariate outcomes include patient-related outcomes (BPI and PROMIS-10 scores) and PJ PGE₂ concentrations at baseline and day 28. Fixed effect covariates include randomized groups, time, and their interactions. Additional secondary analyses include descriptive analysis and statistical comparison of PJ PGE₂ concentrations at baseline and after secretin administration between the various study groups, and correlations between baseline PJ PGE₂ levels, clinical features, and changes in plasma and saliva PGE₂ levels. Changes in daily pain ratings and narcotic use (in morphine equivalents) will be analyzed in comparison to changes in PJ PGE₂ concentrations. Any dropout before Day 28 will be documented and descriptively summarized. Sensitivity analysis on dropout will be conducted in an exploratory manner according to standard missing data analysis procedure for longitudinal data.¹⁹ As a pilot study, we will collect and descriptively analyze data on feasibility, patient compliance and satisfaction, and attrition, in order to inform the possible future study.

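### Change and indomethacin-level correlations are planned without an arm term, so the difference between arms can by itself make them significant if the arms are pooled

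*Combined protocol and SAP*

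**What the plan says.** Section 9.1 lists as secondary efficacy endpoints that changes in salivary and blood PGE2 after study drug "will have statistically significant correlation with changes in PJ PGE₂ concentrations and blood IN levels", and that "Salivary and blood PGE₂ concentrations will have statistically significant correlation with PJ PGE₂ concentrations". The second names no visit. Section 4.1 adds exploratory hypotheses: that peak indomethacin level correlates with the change in pancreatic juice (PJ) PGE2, and that salivary and blood PGE2, both at baseline and as changes, correlate with the juice values.

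On the analysis set, 9.3 says "the entire study population completing the study protocol will be utilized for most analyses". Section 8.2 includes an indomethacin level in the day-28 blood draw without restricting it to one arm. On method, 9.4.3 lists "correlations between baseline PJ PGE₂ levels, clinical features, and changes in plasma and saliva PGE₂ levels" with no arm term.

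Arm appears in two models:
- The repeated-measures MANOVA of 9.4.3: "Fixed effect covariates include randomized groups, time, and their interactions". Its named outcomes are BPI, PROMIS-10 and PJ PGE2.
- The random intercept model of 9.4.2: "Other outcome variables, such as other biomarkers and questionnaire data, can be analyzed in a similar way".

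Two statements frame the use and the expectation. Section 2.2 says that "if correlation is high it may be possible to use these non-invasive biospecimens as surrogates for pancreatic juice in future studies". Section 2.1 says that indomethacin "is an inhibitor of COX-2 and suppresses systemic" PGE2 production.

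**The concern.** The surrogate question is whether a patient with a larger fall in blood or saliva PGE2 also has a larger fall in juice PGE2. The exposure-response question is whether a patient with a higher indomethacin level has a larger fall. Both are questions about patients within an arm.

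A correlation across both arms mixes that association with the difference between arm means. The protocol expects indomethacin to lower PGE2 in juice (its primary hypothesis) and systemically (2.1). If both happen, the indomethacin patients sit lower on both axes, and the two clusters produce a positive correlation on their own. The indomethacin level is the sharper case. Placebo patients should have levels near zero, so a pooled correlation with PGE2 change largely repeats the comparison of arms.

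Neither model with a group term closes the gap. The MANOVA leaves out blood PGE2, saliva PGE2 and indomethacin level. The random intercept model takes one outcome at a time and gives no correlation between fluids.

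At stake is what the next trial takes from this pilot: whether blood or saliva can stand in for endoscopic juice collection, and whether drug level predicts response.

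**Working it through.** **Inputs from the documents (9.2).** 16 per arm, or 12 with data loss; PJ PGE2 centre 307 pg/ml (a median, used as the mean); SD 84 pg/ml; falls of 1/3 and 50%; two-sided alpha 0.05. (Section 9.4.1 prints a threshold of 0.5. That is a separate matter, and 0.05 is used here.)

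**Assumptions, not in the documents.** Baseline to day 28 correlation rho of 0, 0.5 or 0.7; the same SD at both visits and in both arms; the same standardised effect in blood or saliva as in juice (varied in step 4); placebo indomethacin level 0; between-patient CV of the level 30-70%; zero association within each arm.

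**Step 1: the plan's own figures.** No power is stated for any correlation, so the check is on the t-test. Normal approximation, 1/3 fall, n = 16: (307/3)/(84 × √(2/16)) = 102.3/29.7 = 3.446; 3.446 − 1.96 = 1.486; power 0.931 (stated 0.94). With n = 12: 102.3/34.3 = 2.984; power 0.847 (stated 0.85). 50% fall, n = 16: 153.5/29.7 = 5.169; power 0.999 (stated 0.998). The inputs are therefore read correctly. The exact noncentral t gives 0.915, 0.814 and 0.999.

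**Step 2: size of the arm difference in change.** SD of change = 84 × √(2(1 − rho)), and d = 307 × fall / SD of change. For rho 0.5 the SD of change is 84, so d = 102.3/84 = 1.22 or 153.5/84 = 1.83.

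**Step 3: pooled fluid-to-fluid correlation with no within-arm association.** With 1:1 allocation and equal d, expected r = (d²/4)/(1 + d²/4). For d = 1.22: 0.371/1.371 = 0.27. The critical |r| for 32 patients is 0.349. Rejection rates are from 20,000 simulated trials per row:

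| Fall | rho | d | Expected r | Significant, 16/arm | Significant, 12/arm |
|---|---|---|---|---|---|
| 1/3 | 0 | 0.86 | 0.16 | 14% | 11% |
| 1/3 | 0.5 | 1.22 | 0.27 | 34% | 26% |
| 1/3 | 0.7 | 1.57 | 0.38 | 63% | 50% |
| 50% | 0 | 1.29 | 0.29 | 40% | 31% |
| 50% | 0.5 | 1.83 | 0.46 | 82% | 69% |
| 50% | 0.7 | 2.36 | 0.58 | 98% | 94% |

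The partial correlation adjusted for arm rejects in about 5% of trials in every row.

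**Step 4: unequal effects.** With juice d = 1.22, 16 per arm, and d in the second fluid of 0, 0.6, 1.22, 2 and 3, the pooled test is significant in 5%, 13%, 33%, 60% and 76% of trials.

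**Step 5: indomethacin level against PGE2 change.** Expected r = −(d/4)/√((1/4 + CV²/2)(1 + d²/4)). For d = 1.22 and CV 30%: −0.305/√(0.295 × 1.371) = −0.48. For CV 70%: −0.305/√(0.495 × 1.371) = −0.37. Simulated with log-normal levels, 16 per arm and rho 0.5, the pooled test is significant in 65-86% of trials at a 1/3 fall and about 90-99% at a 50% fall. In the indomethacin arm alone it is about 5%.

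**The case against.** - **Pooling is not stated.** A reader might infer that the plan commits itself to pooling both arms. It does not. Section 9.1 names no analysis set, 9.3 covers most analyses rather than all, and the secondary objective speaks of changes induced by the drug, which allows a reading confined to the indomethacin arm. This stands: pooling is the default reading, not a stated rule. The missing arm term needs the same repair either way.
- **Baseline correlations are planned.** A reader might infer that the whole surrogate question is compromised. It is not. The baseline correlations in 4.1 precede any drug and cannot be created by its effect. Only change and day-28 correlations are exposed.
- **Significance is not the surrogate criterion.** Section 2.2 asks for a high correlation and draws only a tentative conclusion. At rho 0.5 the artefact gives an expected r of 0.27 to 0.46, so r² is 0.07 to 0.21, which few would call high. This stands against any claim that the next trial would adopt an uninformative surrogate on this ground alone. The bias still enters r itself, and 9.1 sets statistical significance as its criterion.
- **The result is conditional.** At a 1/3 fall and rho 0.5, about two trials in three show no significant fluid-to-fluid correlation. The documents give no effect size for blood or saliva. This stands, hence the ranges. Nor is it strictly a type I error: the pooled correlation is truly non-zero, but it answers a different question.
- **The stakes are modest.** Section 4.1 calls these hypotheses exploratory, and the indomethacin level is described there as a compliance measure. That limits the severity. It does not make a pooled correlation interpretable.

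**Conclusion.** The point holds in a conditional form. The change and indomethacin-level correlations have no arm term, pooling is the default reading, and no planned model supplies an arm-adjusted version. Followed that way, the arm difference can by itself produce a significant correlation that says nothing about patients within an arm. With 16 per arm, the chance spans 14-98% for fluid against fluid over falls of 1/3 to 50% and rho of 0 to 0.7, given equal standardised effects. It needs a drug effect in both fluids; without one in the second fluid there is no inflation. The problem is greatest for indomethacin level, at about 65-99% over the same falls with rho 0.5, CV 30-70% and placebo levels at zero. The documents do not support saying that a significant result is certain, or that every blood and saliva correlation is affected. As these are secondary and exploratory analyses of a pilot, the change should be made, but it does not bear on the primary comparison.

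**What to change.** In 9.1 and 9.4.3:
1. Define the correlations of PJ PGE2 change with blood and saliva PGE2 change, and any day-28 level correlations, as partial correlations adjusted for randomized arm, with 95% confidence intervals and estimates by arm.
2. Restrict every indomethacin-level correlation to the indomethacin arm. This covers juice, blood and saliva PGE2 change, including the blood and saliva test in 9.1.
3. Report the baseline level correlations separately.
4. Base the surrogate statement in 2.2 on these estimates and their intervals.

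No new data or visits are needed. The partial correlation costs one degree of freedom: with 32 completers the critical |r| moves from 0.349 to 0.355, and a true r of about 0.48 is needed for 80% power. The indomethacin-level analyses pay more. With 16 patients, |r| of about 0.50 is needed for p < 0.05 and a true r of about 0.65 for 80% power; with 12 patients the critical |r| is about 0.58. They should be presented as estimates with wide intervals.
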